12.5.3.3 Change from Baseline in CD8⁺ TILs and Regulatory T-Cells in Tumour Tissue

For the key secondary endpoints of CD8⁺ TILs and regulatory T-cells (FOXP3) it is hypothesised based on the mode of action of setanaxib that there will be an increase in CD8⁺ TILs and a decrease in FOXP3. These secondary efficacy analyses will repeat the analysis described for CAFs level in Section 12.5.3.2.

12.5.3.4 Sensitivity Analyses

In anticipation of small numbers of progression events within the subgroups of HPV status, a sensitivity analysis of the methods described in Section 12.5.3.1, will be repeated without HPV status.

12.5.4 Other Secondary Efficacy Analyses

The secondary estimand attributes are given in Section 9.1.2.

12.5.4.1 Objective Response Rate (ORR) and Disease Control Rate (DCR)

The point estimates of ORR and DCR (see Sections 10.9.3 and 10.9.5 respectively) will be summarised using descriptive statistics along with associated 90% Agresti-Coull CIs for each treatment group.

12.5.4.2 Duration of Response (DoR) and Overall Survival (OS)

The secondary endpoints of DoR and OS will not be formally compared between the treatment groups, but will be summarised using Kaplan-Meier plots presented by treatment group.

Specifically, for OS, the median, upper quartile, lower quartile OS and the proportion of patients who are alive at 3, 6, and 12 months will be presented along with 80% Wald CIs, obtained using the Brookmeyer-Crowley method (1982).

DoR will only be presented if there are at least 5 responders in either treatment group, otherwise this data will be listed only.

Censoring rules for both DoR and OS are described in Sections 10.9.4 and 10.8.2 respectively.

12.5.4.3 Gene Expression

For the secondary endpoint of changes in patterns of gene expression and differential gene expression in tumour tissue, analysis will be described in the standalone biomarker analysis plan.

12.5.4.4 Change from Baseline in PD-L1 Expression in Tumour Tissue

The analysis for the key secondary endpoint of PD-L1 expression will repeat the analysis described for CAFs level in Section 12.5.3.2.

12.5.4.5 Sensitivity Analyses

There are no planned sensitivity analyses of the other secondary endpoints.

12.5.5 Supportive Analyses

It was noted during enrolment that one site, [name], has enrolled a large proportion of patients. To explore a potential site effect, a supportive site subgroup analysis will evaluate the effect of setanaxib on the best percentage change in tumour size using an ANCOVA model, including the same covariates as described for the primary analysis in Section 12.5.2.2, repeated for each site subgroup ([name] vs Other). The number of patients, unadjusted mean, and adjusted LS means for each treatment group will be presented, together with the difference in adjusted LS means and 80% CI. No p-value will be presented for these analyses.

There are no further efficacy analyses planned, see Section 6.1.1 for additional details.

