8.0 Study Design

This is a randomised, double-blind, placebo-controlled, proof-of-concept, Phase 2 study assessing setanaxib coadministered with pembrolizumab in patients with recurrent or metastatic SCCHN. The safety and efficacy of setanaxib 800 mg BID will be assessed against matching placebo over up to 105 weeks of treatment. The design is depicted in Figure 1.

AE=adverse event; CAFs=cancer-associated fibroblasts; IV=intravenously; PFS=progression-free survival; PO=per os (orally, or via either a feeding tube or a percutaneous endoscopic gastrostomy device in case patients are unable to swallow tablets); q3w=every 3 weeks; R=randomisation; RECIST v1.1=response evaluation criteria in solid tumours version 1.1 * For patients with a suitable archival tumour biopsy sample available, the archival sample may be used to assess CAFs level and determine eligibility (Note: this can only be performed after the patient has provided signed informed consent). This will not dispense from the need for a recent pre-study tumour biopsy.

The study plans to randomise approximately 50 patients at up to approximately 35 investigational centres in North America and Europe, to the IMP, according to a 1:1 randomisation ratio, stratified by HPV status. Depending on the number of patients providing evaluable Week 9 biopsy and imaging data, up to an additional 20 patients (making a maximum of 70 patients) may be randomised to ensure an adequate amount of data is available for the efficacy and biomarker analyses.

The study will consist of an up to 35-day Screening Period, an up to 24-month Treatment Period (Day 1 to Week 105), and a 28-day Safety Follow-up Period. The total duration of the study for patients remaining in the study until their final follow-up assessment will be up to approximately 114 weeks (approximately 2 years and 2 months).

All patients included in this study will receive pembrolizumab, with setanaxib or placebo given as add-on therapy to a recognised and approved standard-of-care agent.

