8.1 Sample Size Considerations

An overall sample size of approximately 50 patients (25 per treatment group) is considered sufficient to assess the primary endpoint of the best percentage change in tumour size following treatment with setanaxib when administered with pembrolizumab, versus placebo when administered with pembrolizumab, in patients with recurrent or metastatic SCCHN. With 25 patients per treatment group, using a 2-sided t-test, there will be 85% power to detect a 20% mean difference between the treatment groups in best percentage change in tumour size, with an estimated SD of 30% and a 2-sided alpha of 20%. To mitigate risks from a higher than expected number of patients discontinuing the study early or declining to have imaging or biopsies at Week 9, up to an additional 20 patients (making a maximum of 70 patients) may be randomised.

The key secondary endpoints of numbers of CAFs, CD8⁺ TILs, and regulatory T-cells in tumour tissue and gene expression analysis in tumour tissue will be used to determine proof of concept. With 25 patients per treatment group, there will be 90% power to detect a limit fold change (LFC) of more than 1.5 in gene sequencing endpoints measured in tumour tissue, assuming at least 20 patients have an evaluable Baseline and post-Baseline tissue sample.

For the key secondary endpoint of PFS, if the true hazard ratio for PFS is 0.5, approximately 38 progression events as defined by RECIST v1.1 will be required to have > 80% power to demonstrate a statistically significant difference in PFS with 2-sided p<0.2.

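### SAP 12.5.5 explores a site effect without reporting the difference between the two site-group treatment effects; side-by-side 80% intervals are a poor guide to it

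*SAP*

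**What the plan says.** SAP 12.5.5 (Supportive Analyses) records that one site "has enrolled a large proportion of patients" and sets out to explore whether there is a site effect. It fits an ANCOVA for best percentage change in tumour size, "including the same covariates as described for the primary analysis in Section 12.5.2.2, repeated for each site subgroup", the two subgroups being that site and all others. Each fit yields patient counts, raw and adjusted means by arm, and the adjusted treatment difference with an 80% CI. The section adds: "No p-value will be presented for these analyses".

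The primary model in SAP 12.5.2.2 has treatment, baseline tumour size and, if each HPV level has at least 10 patients in each arm, HPV status. It has no site term. SAP 12.0 points to 12.5.5 for any site effect and otherwise rules one out, and 12.5.5 closes by planning no further efficacy analyses. So no treatment-by-site term, and no contrast between the two subgroup effects, appears anywhere in the plan.

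The site's share of patients is not stated. Randomisation is "according to a 1:1 randomisation ratio, stratified by HPV status" (SAP 8.0), so arm balance within the site is not enforced by design.

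**The concern.** Whether the treatment effect depends on site is a question about the difference between two treatment effects. The plan prints each effect with its own interval and leaves the comparison to the reader. The natural shortcut is to see whether each interval excludes zero. In small subgroups that shortcut mostly reflects limited power within each subgroup, not a difference between them. If one interval excludes zero and the other does not, the large site may be thought to drive the result, or to dilute it, when nothing differs. Conversely, two intervals that agree about zero say little about how large a difference remains possible, because the uncertainty of that difference is not shown.

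The SAP already uses the appropriate device elsewhere: in 12.5.3.1 it considers a treatment-by-HPV interaction term in the Cox model for PFS.

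**Working it through.** **Inputs.** From SAP 8.1: about 50 patients (25 per arm), at most 70; true difference 20 points; SD 30; two-sided alpha 20%, which matches an 80% CI. Assumed, because the documents do not say: the large site holds 20-50% of patients, the arms are equal within each site group, and the true effect and SD are the same in both groups.

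**Step 1: reproduce the plan's figure.** SAP 8.1 states "there will be 85% power to detect a 20% mean difference between the treatment groups in best percentage change in tumour size". With 25 per arm the standard error is 30 × √(2/25) = 8.49, the noncentrality is 20/8.49 = 2.36, and noncentral-t power at two-sided 20% is 85.4%. The stated figure is reproduced.

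**Step 2: chance that the two intervals disagree about zero.** Let p and q be the probabilities that the 80% CI excludes zero in the large site and in the other sites, each from the same noncentral-t calculation. The subgroups contain different patients, so the results are independent and

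P(disagree) = p(1 − q) + q(1 − p).

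With 50 patients and a common effect of 20 points:

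| Site share | n per arm (site / other) | p | q | Disagree | Both exclude zero | Neither |
|---|---|---|---|---|---|---|
| 20% | 5 / 20 | 0.40 | 0.79 | 56% | 32% | 13% |
| 30% | 7.5 / 17.5 | 0.49 | 0.75 | 50% | 37% | 13% |
| 40% | 10 / 15 | 0.57 | 0.70 | 47% | 40% | 13% |
| 50% | 12.5 / 12.5 | 0.64 | 0.64 | 46% | 41% | 13% |

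For example, at 40%: 0.57 × 0.30 + 0.70 × 0.43 = 0.17 + 0.30 = 0.47. Simulating two separate ANCOVAs with whole numbers of patients gave 58%, 51%, 48% and 46%.

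**Step 3: sensitivity.**
- 70 patients, effect 20: 52%, 44%, 39% and 38% for shares of 20%, 30%, 40% and 50%.
- 50 patients, other common effects: 45-46% at 10 points, 50-54% at 15, 35-51% at 25.
- No treatment effect: p = q = 0.20, so 2 × 0.20 × 0.80 = 32%, whatever the share or total.
- Stricter definitions (50 patients, effect 20): opposite signs 9-16%, non-overlapping 80% CIs 7-9%.

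**Step 4: what the contrast would show.** With a per arm in the site and b per arm elsewhere, the standard error of the difference between the two effects is 30 × √(2/a + 2/b). With 50 patients:
- 50% share: 30 × √(2/12.5 + 2/12.5) = 17.0; 80% half-width 1.28 × 17.0 ≈ 22 points.
- 20% share: 30 × √(2/5 + 2/20) = 21.2; 80% half-width 1.28 × 21.2 ≈ 27 points.

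When the effects are equal, the 80% CI for this contrast excludes zero in 20% of trials, by construction. In simulation with 50 patients and effect 20, among trials where the two subgroup intervals disagreed about zero, the contrast's 80% CI excluded zero in only 24-36%. If the effects truly differed by 20 points, it would exclude zero in 38-47% of trials (normal approximation).

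**The case against.** The analysis is labelled supportive, is meant to explore, carries no decision rule and shows no p-value. Nothing in the SAP tells anyone to compare the intervals by whether each excludes zero, so the misreading would be the reader's. That is fair and keeps the priority low, but omitting a p-value does not stop an 80% CI from being read against zero.

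A reader might infer that the analysis cannot answer its own question. The documents do not support that. The two estimates are independent, so the contrast is the difference of the two printed estimates, and its approximate half-width is the square root of the sum of the squared printed half-widths. The plan omits a derivable line; it does not make the line unobtainable.

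A reader might also infer that disagreement is the usual pattern whenever there is no site effect. That is true of the four shares in the table, but not in general. With 70 patients split 10 and 25 per arm, both intervals exclude zero in 48.9% of trials and they disagree in 44.9%. With no treatment effect, both include zero in 0.80 × 0.80 = 64%.

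Finally, one might say that HPV would almost always drop out of the subgroup models. If the 10-per-cell rule were re-applied within each subgroup, each model would need at least 4 × 10 = 40 patients, so HPV in both would need 80, above the maximum of 70. But the SAP does not say that the rule is re-applied, and HPV may drop out of the primary model too, in which case the models would match. This point is not relied on.

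The contrast is also imprecise, so the practical gain is modest. That stands, but the imprecision is itself something the reader should see.

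**Conclusion.** The point holds in a conditional form. SAP 12.5.5 does not report the difference between the two site-group treatment effects, and no other section fills the gap. On the plan's own effect and SD, with 50 patients and an assumed site share of 20-50%, equal true effects still give one 80% CI excluding zero and one including it in about 46-56% of trials. The range is 38-52% with 70 patients, and the figure is 32% with no treatment effect. These figures concern that one definition of disagreement. Opposite signs or non-overlapping intervals are much rarer, about 7-16% with 50 patients and a 20-point effect, though with no treatment effect opposite signs occur half the time.

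The site share and equal arms within site groups are assumptions. The primary analysis is not affected. This is a worthwhile, low-priority improvement.

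**What to change.** In SAP 12.5.5, replace the two fits by one ANCOVA on the primary analysis population with treatment, baseline tumour size, HPV status (under the primary model's existing 10-per-cell rule), site group and treatment-by-site-group. Report the treatment difference in each site group and the contrast between them, each with an 80% CI and no p-value. Add a sentence saying that the subgroup intervals are not to be compared by whether each excludes zero.

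The cost is small but not nil. The single model assumes a common residual variance and baseline slope across site groups, which separate fits avoid. One table shell needs a minor update, and the SAP has already been versioned for final signature. If the separate fits are preferred, keep them and add one line: the difference between the two estimates with its 80% CI. No new data or patients are needed either way.

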12.6 Safety Analyses

Safety analyses will be conducted using the Safety Analysis Set and will be summarised descriptively, unless otherwise noted in the sections that follow. All safety related outputs will be produced at the time of both the primary analysis and the updated analysis (see Section 12.5).

12.6.1 Adverse Events

All AEs recorded in the eCRFs will be coded using MedDRA (version 25.0 or higher) and graded using the National Cancer Institute (NCI) Common Terminology Criteria for Adverse Events (CTCAE) v5.0. Events that are not coded at the time of a data snapshot will be included and presented using the verbatim term (in uppercase letters) as the PT and "UNCODED" for the SOC. Events with missing severity at the time of the data snapshot will be left as missing.

Summary tables will present the number of events reported as well as the number and percentage of patients reporting them, unless otherwise specified.

An overall summary of TEAEs, will be provided, including line items for the following;

- TEAEs
- Severe (CTCAE Grade ≥3) TEAEs
- TEAEs Related to IMP
- TEAEs with a Fatal Outcome
- TEAEs of Special Interest (see Section 10.10.5)
- Serious TEAEs
- Serious TEAEs Related to IMP
- TEAEs Leading to a Reduction of the IMP Dose
- TEAEs Leading to the Discontinuation of IMP (Drug Withdrawal)
- TEAEs Leading to Discontinuation from the Study

A summary of TEAEs by SOC, PT and maximum severity will also be presented by patient (not events). Patients who experience multiple events within the same SOC/PT will be counted only once in the most severe grade.

The following types of TEAEs will also be summarised by SOC and PT:

- TEAEs
- Severe (CTCAE Grade ≥3) TEAEs
- TEAEs Related to IMP
- TEAEs of Special Interest
- TEAEs Leading to the Discontinuation of IMP (Drug Withdrawal)

• TEAEs Leading to Discontinuation from the Study

TEAEs will also be summarised by PT only.

All AEs (including non-TEAEs) will be listed and any AE occurring after a patient has received another anti-cancer therapy (after discontinuation of study treatment) will be flagged.

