Two Phase 3 studies have further evaluated the efficacy and safety of pembrolizumab in patients with recurrent or metastatic SCCHN. In KEYNOTE-040 (Cohen et al 2019), 495 patients with SCCHN who had progressed during or after platinum-containing treatment for recurrent or metastatic disease (or both), or whose disease recurred or progressed within 3 to 6 months of previous multimodal therapy containing platinum for locally advanced disease, were randomly assigned to treatment with pembrolizumab 200 mg q3w or investigator's choice of standard doses of methotrexate, docetaxel or cetuximab ("standard-of-care"). In this study, the median OS was 8.4 months with pembrolizumab and 6.9 months with standard-of-care (p=0.0161). Fewer patients treated with pembrolizumab than with standard-of-care had Grade 3 or worse treatment-related AEs (33 [13%] of 246 pembrolizumab-treated patients versus 85 [36%] of 234 standardof-care-treated patients). The most common treatment-related AE was hypothyroidism in 33 (13%) patients with pembrolizumab and fatigue in 43 (18%) patients treated with standard-of-care. Treatment-related death occurred in 4 patients treated with pembrolizumab (unspecified cause, large intestine perforation, malignant neoplasm progression, and Stevens-Johnson syndrome) and 2 patients treated with standard-of-care (malignant neoplasm progression and pneumonia).

KEYNOTE-048 was a Phase 3, randomised, open-label study conducted in patients with recurrent or metastatic SCCHN that was not curable by local therapy (Burtness et al 2019). Patients were randomly allocated (1:1:1) to pembrolizumab alone, pembrolizumab plus a platinum and 5-fluorouracil (pembrolizumab with chemotherapy), or cetuximab plus a platinum and 5-fluorouracil (cetuximab with chemotherapy); randomisation was stratified by PD-L1 expression, p16 status, and performance status. A total of 882 patients were allocated to receive pembrolizumab alone (n=301), pembrolizumab with chemotherapy (n=281), or cetuximab with chemotherapy (n=300); of these, 754 (85%) patients had a PD-L1 combined positive score (CPS) of 1 or more and 381 (43%) had CPS of 20 or more.

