In addition, for patients with a suitable archival tumour biopsy sample available, the archival sample may be used to assess CAFs level and determine eligibility (Note: this can only be performed after the patient has provided signed informed consent). This will not dispense from the need for a recent pre-study tumour biopsy, collected during or within 30 days prior to the Screening Period, for patients eligible for the study.

To be considered suitable for determination of CAF levels, archival biopsy must have been collected within 6 months prior to the Screening Visit (Visit 1), and the patient must

have received no further anti-cancer therapy since then (see Section 5.2.2 for more details on suitability). Elevated CAF levels in suitable archival tumour tissue will meet the eligibility requirement based on CAF levels, but an additional pre-study biopsy (during or within 30 days of the Screening Period) is needed for reliable Baseline biomarker analysis.

Eligible patients will be randomised to the investigational medicinal product (IMP) setanaxib 800 mg BID, or placebo, according to a 1:1 randomisation ratio, stratified by HPV status. See Section 6.3 for further details on the method of assigning patients to the treatment groups, and see Section 6.4 for further details on the dose and administration of setanaxib and placebo. Treatment with pembrolizumab will be initiated on the same day (Day 1) as the first dose of IMP, and will be administered according to current clinical guidelines and labelling, ie, 200-mg intravenous (IV) infusion q3w. See Section 6.7 for further details on the dose and administration of pembrolizumab.

Treatment with pembrolizumab will continue until: RECIST v1.1-defined disease progression as determined by the investigator (Eisenhauer et al 2009), unacceptable toxicity, or a maximum of 24 months. If progression is suspected, but not confirmed, study treatment may continue until confirmation of radiological progression.

Treatment with setanaxib or placebo will continue throughout the period of pembrolizumab therapy. When pembrolizumab is discontinued, blinded study treatment will be discontinued at the same time.

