8.3 Sample Size

An overall sample size of approximately 50 patients (25 per treatment group) is considered sufficient to assess the primary endpoint of the best percentage change in tumour size following treatment with setanaxib when administered with pembrolizumab, versus placebo when administered with pembrolizumab, in patients with recurrent or metastatic SCCHN. With 25 patients per treatment group, using a 2-sided t-test, there will be 85% power to detect a 20% mean difference between the treatment groups in best percentage change in tumour size, with an estimated SD of 30% and a 2-sided alpha of 20%. To mitigate risks from a higher than expected number of patients discontinuing the study early or declining to have imaging or biopsies at Week 9, an additional up to 20 patients (making a maximum of 70 patients) may be randomised.

The key secondary endpoints of numbers of CAFs, CD8⁺ TILs, and regulatory T-cells in tumour tissue, and gene expression analysis in tumour tissue will be used to determine proof-of-concept. With 25 patients per treatment group, there will be 90% power to detect a limit fold change (LFC) of more than 1.5 in gene sequencing endpoints measured in tumour tissue, assuming at least 20 patients have an evaluable Baseline and post-Baseline tissue sample.

For the key secondary endpoint of PFS, if the true hazard ratio for PFS is 0.5, at least 38 progression events as defined by RECIST v1.1 will be required to have >80% power to demonstrate a statistically significant difference in PFS with 2-sided p<0.2.

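### AE and AESI tables have no time-at-risk denominator although treatment runs to progression, so at the planned PFS effect background hypothyroidism could look about 1.2 to 1.5 times as frequent on setanaxib at the planned analyses with no drug effect

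*SAP*

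**What the plan says.** **Scale.** SAP 12.6.1: "Summary tables will present the number of events reported as well as the number and percentage of patients reporting them, unless otherwise specified". The AESI tables follow this rule. SAP 12.3.1 tabulates duration of exposure separately and does not use it as a denominator for adverse events.

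**Time at risk.** Protocol 3.1 continues pembrolizumab to RECIST progression, unacceptable toxicity or 24 months, and ties study drug to it: "Treatment with setanaxib or placebo will continue throughout the period of pembrolizumab therapy". SAP 10.10.1 counts TEAEs to 28 days after the last dose.

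**Planned effect.** SAP 8.1: "For the key secondary endpoint of PFS, if the true hazard ratio for PFS is 0.5". Protocol 8.3 states the same value.

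**Background.** Protocol 1.1.3, on a Phase 3 trial in patients mostly pre-treated with platinum: "The most common treatment-related AE was hypothyroidism in 33 (13%) patients with pembrolizumab". Section 1.3, Table 2 names thyroid disorders as the potential overlapping toxicity of the combination.

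**Timing.** Under SAP 12.5 and 12.6, safety outputs are produced at the primary analysis (about 15 weeks after enrolment ends) and at the updated analysis (about 38 progression events). After that, SAP 6.0 plans only selected listings, although SAP 8.4 mentions an updated safety analysis if the final lock comes later.

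**The concern.** When treatment stops at progression, a drug that delays progression also lengthens the period in which adverse events are counted. A crude percentage then mixes the event rate with the length of observation. If setanaxib works as the PFS sizing supposes, its arm collects more background hypothyroidism even with an unchanged monthly risk. That is the toxicity the protocol singles out for the combination. A reader of the planned tables could not tell an excess caused by the drug from one caused by longer treatment. If setanaxib shortened treatment, the distortion would run the other way; no size is worked out for that case.

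**Working it through.** **1. The plan's own figure.** Protocol 8.3 takes a hazard ratio of 0.5 and a two-sided significance level of 0.2, and concludes: "at least 38 progression events as defined by RECIST v1.1 will be required to have >80% power". Patients are allocated 1:1 (Protocol 3.1). By Schoenfeld's formula, events = 4(z₀.₉₀ + z₀.₈₀)² / (ln 0.5)² = 4(1.2816 + 0.8416)² / 0.4805 = 37.5, so 38, with power 80.4%. The figure reproduces, so 0.5 is the effect the trial is sized for.

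**2. Inputs.**
- From the documents: hazard ratio 0.5, placebo hypothyroidism 13%, 24-month cap, window w = 28 days = 0.92 month.
- Assumed: time to stopping is exponential with rate λ on placebo and λ/2 on setanaxib; treatment stops only at progression or the cap; the hypothyroidism hazard h is constant and equal in both arms; the placebo median is 2.1 to 6 months. The low end is the median PFS of the single-arm pembrolizumab trial in Protocol 1.1.3.

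**3. Complete follow-up.** The crude proportion is

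P = 1 − e^(−hw) [ λ/(λ+h) · (1 − e^(−24(λ+h))) + e^(−24(λ+h)) ].

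Example, placebo median 3 months: λ = ln 2 / 3 = 0.2310 per month, and P = 0.13 gives h = 0.0279. On setanaxib λ = 0.1155, so the bracket is 0.812, e^(−hw) is 0.975, and P = 1 − 0.975 × 0.812 = 20.9%. The ratio is 20.9/13 = 1.61.

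| Placebo median (months) | Placebo | Setanaxib | Crude ratio |
|---|---|---|---|
| 2.1 | 13% | 20.8% | 1.60 |
| 3 | 13% | 20.9% | 1.61 |
| 4 | 13% | 20.5% | 1.57 |
| 6 | 13% | 19.3% | 1.48 |

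Using instead the setanaxib exposure anticipated in Protocol 3.2 (80%, about 50% and about 30% still treated at 3, 6 and 12 months), with its square for placebo, gives 1.58 to 1.60. First events per patient-month estimate h in both arms, so the exposure-adjusted ratio is 1.0 throughout.

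**4. The planned cut-offs.** The same model is cut at each patient's available follow-up, with uniform accrual over 6 to 24 months (assumed; the documents give no accrual period) and placebo medians of 2.1 to 4 months.

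| Analysis | Crude ratio, no drug effect |
|---|---|
| Primary, 15 weeks after enrolment ends | 1.18 to 1.49 |
| 38 events, 50 patients | 1.30 to 1.44 |
| 38 events, 70 patients | 1.16 to 1.38 |

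**5. Weaker assumptions, complete follow-up.**
- Hazard confined to the first 3, 6 or 12 months (placebo medians 2.1 to 4): 1.06 to 1.10, 1.16 to 1.27, 1.35 to 1.48.
- A share s of placebo-arm stopping unrelated to progression and equal in both arms, so the setanaxib stopping rate is λ[s + 0.5(1 − s)], with background 33/246 = 13.4%: s = 20% gives 1.36 to 1.42; s = 40% gives 1.25 to 1.28.
- Background from 5% to 20%: 1.45 to 1.68.

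**6. In patients.** With 25 per arm, 13% versus 20.8% is about 3 versus 5 patients.

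**The case against.** **The tables are descriptive.** Protocol 8.4.6 and SAP 12.6 plan no safety test, and no decision rule uses these percentages. Three versus five patients gives a Fisher p-value of 0.70. With identical true percentages of 13.4%, chance alone puts the setanaxib count at 1.6 times the placebo count or more in about 27% of trials. This stands, and it limits how much rests on the point. A reader might infer that the tables would give the wrong safety answer; the documents do not support that. Still, percentages set side by side are what readers compare, and a known source of difference should be visible.

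**By-visit laboratory data help.** SAP 12.6.3 summarises TSH, free T4 and haemoglobin by analysis visit, which compares the arms at equal times. That helps with the laboratory values but does not correct the AESI percentages.

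**The inputs are favourable to the concern.** The hazard ratio of 0.5 is a conditional sizing value, not a forecast. Protocol 4.3.1 lists many reasons for stopping other than progression. The 13% is treatment-related hypothyroidism in mostly pre-treated patients, whereas this trial is first-line and defines the AESI by TSH (Protocol 7.1.5) or MedDRA codes (SAP 15.2). These objections stand, and the range above reflects the stopping and onset assumptions.

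**Two stronger readings fail.** A reader might take 1.6 as the expected distortion, but that needs follow-up of every patient to the end of treatment, which the planned full outputs do not have. A reader might also extend the figure to anaemia. The documents give a pembrolizumab background for hypothyroidism only; the anaemia concern comes from dog studies of setanaxib, so no size can be attached to it.

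**A rate also assumes a constant hazard.** True. If onset is early, a person-time rate dilutes events in the longer-treated arm. This is why a curve is needed as well. The separate IDMC SAP was not available and may contain more.

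**Conclusion.** The omission is real and should be corrected, but it is modest. No time-at-risk summary is planned for any adverse event, although observation ends with progression. If the hazard ratio is 0.5, hypothyroidism has a constant and equal hazard with 13% on placebo, and only progression or the 24-month cap stops treatment, the crude ratio with no drug effect is about 1.2 to 1.5 at the planned primary and 38-event analyses. It rises to about 1.5 to 1.6 with complete follow-up and falls to about 1.1 to 1.3 with onset confined to the first 3 to 6 months or a sizeable share of unrelated stopping. The direction is the same in every scenario examined. The size rests on assumptions about hazard shape, stopping and accrual that the documents do not supply.

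**What to change.** In SAP 12.6.1, keep the crude tables as descriptive and add, by arm:

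1. Exposure-adjusted incidence rates for all TEAEs, Grade ≥3 TEAEs and each AESI: patients with a first event divided by patient-years at risk. Time at risk runs from first dose to the earliest of first event, end of the TEAE window, death or data cut-off.
2. A cumulative-incidence curve of time to first hypothyroidism AESI and to first anaemia AESI, censored at the end of each patient's TEAE window or the data cut-off, with death as a competing event. Treatment discontinuation should not be a competing event, because that would bring the dependence on exposure back.

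Read the two AESIs mainly from the curves, which do not need a constant hazard.

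The cost is a few extra outputs from event and dosing dates already collected. The estimates will be imprecise with 25 patients per arm, and the rate is only approximate if the hazard changes over time. No dose, stopping rule or clinical procedure is affected.
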